1 INTRODUCTION

This statistical analysis plan (SAP) documents the variables to be analysed and the statistical methods of the planned analyses and outlines the statistical programming specifications for the tables, figures and listings (TFLs). Any deviations after database lock, reasons for such deviations and all alternative or additional statistical analyses that may be performed, will be described in an SAP addendum and discussed in the Clinical Study Report (CSR). Any changes to this SAP prior to database lock will be described in a new version of the SAP.

The analyses described in this SAP are based upon the following study documents:

- Clinical Study Protocol (CSP), Version 1.0 (September 21, 2021)

The content of this SAP is compatible with the International Council for Harmonization (ICH)/Food and Drug Administration (FDA) E9 Guidance documents.

2 STUDY OBJECTIVES AND ENDPOINTS

2.1 Primary Objective

Primary Objective:

To evaluate the PK comparability between AZD7442 administered as a single IM dose (co-formulation) (AZD8895 + AZD1061) and two separate IM doses (AZD8895 and then AZD1061) (clonal cell line material of AZD8895 and AZD1061) of the individual monoclonal antibodies (mAbs) in healthy adult participants

To evaluate the PK comparability between AZD7442 administered as a single IM dose (co-formulation) (AZD8895 + AZD1061) and two separate IM doses (AZD8895 and then AZD1061) (cell pool material of AZD8895 and AZD1061) of the individual mAbs in healthy adult participants

To evaluate the PK comparability between the clonal cell line material and the cell pool material of AZD7442 administered as two

Endpoint:

- AUC_{inf} (final analysis), AUClast, C_{max}, and AUC_{0-91d}
- AUC_{inf} (final analysis), AUClast, C_{max}, and AUC_{0-91d}
- AUC_{inf} (final analysis), AUClast, C_{max}, and AUC_{0-91d}

separate sequential IM doses (AZD8895 and then AZD1061) of the individual mAbs in healthy adult participants

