On the day of IMP administration (Day 1), participants should follow a diet, which excludes all alcohol (from at least 72 hours prior to dosing) and caffeinated products (from at least 24 hours prior to dosing). Participants are not required to abstain from food and drink intake until 45 minutes to 1 hour before IMP administration.

Expected Duration of the Study

The total duration of the study for a participant will be approximately 389 days comprising of a Screening Period that can last up to 28 days, Treatment Period of 1 day, and a Follow-up Period of 360 days.

Targeted Study Population

This study will be conducted in healthy volunteers, who may be male or female, ≥ 18 years of age, weighing ≥ 50 to ≤ 110 kg, and with a body mass index of ≥ 18 to ≤ 30 kg/m².

Participants should be either non-vaccinated against SARS-CoV-2 infection or vaccinated with the last vaccine dose received at least 14 calendar days before IMP dose. Participants will be allowed to receive anti-COVID-19 vaccination during the study, however, should wait 14 days after their dose of IMP. Participant vaccination status will be documented throughout the study in the eCRF.

All participants must have negative results for SARS-CoV-2 RT-PCR test ≤ 3 days prior to randomization or negative results for rapid SARS-CoV-2 antigen test on day of randomization. Participants with a medical history of infection with SARS or Middle East Respiratory Syndrome or with any clinical signs or symptoms consistent with COVID-19 will be excluded from the study.

Outcome Endpoints

Safety Endpoints:

Safety variables will include

- AEs and SAEs.
- Vital signs (systolic and diastolic blood pressure and pulse rate).
- 12-lead ECGs.
- Physical examination.
- Laboratory assessments (hematology, clinical chemistry, and urinalysis).

Viral serology, drugs of abuse and alcohol will be assessed for eligibility. Coagulation, FSH (to confirm postmenopausal status for female participants) and pregnancy testing (for all female participants of childbearing potential), and use of concomitant medication will also be assessed and reported.

Pharmacokinetic Endpoints:

Where possible, PK parameters will be assessed from serum concentrations for the individual mAbs AZD8895 and AZD1061, as well as for the sum of the individual mAbs (AZD8895 + AZD1061), referred to as AZD7442.

- Primary PK parameters: AUCinf, AUClast, and Cmax.

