- Secondary PK parameters: Tmax, AUC0-31d, AUC0-61d, AUC0-91d, AUC0-181d, tlast, t½λz, CL/F, and Vz/F.

Additional PK parameters may be determined where appropriate.

Exploratory Endpoints:

- CCI

Statistical Methods

Analysis Sets

The safety analysis set will include all participants who were randomized and received any amount of IMP. The PK analysis set will consist of all participants in the safety analysis set who received IMP and have evaluable serum PK data, with no important protocol deviations thought to impact on the analysis of the PK data. The Randomized Set will consist of all participants randomized into the study.

Presentation and Analysis of Pharmacokinetic Data:

The serum concentrations and PK parameters will be listed and presented in tabular and graphical form, as appropriate for the individual mAbs AZD8895 and AZD1061, as well as for the sum of the individual mAbs of AZD7442 (AZD8895 + AZD1061). The serum concentrations for each scheduled time point will be summarized by treatment group, treatment group and injection site, treatment group and bodyweight category, and treatment group, injection site, and bodyweight category using appropriate descriptive statistics, based on the PK analysis set for the individual mAbs AZD8895 and AZD1061, as well as for the sum of the individual mAbs of AZD7442 (AZD8895 + AZD1061). The PK parameters will be derived using non-compartmental methods for the individual mAbs AZD8895 and AZD1061, as well as for the sum of the individual mAbs of AZD7442 (AZD8895 + AZD1061). All PK parameters will be summarized by treatment group, treatment group and injection site, treatment group and bodyweight category, and treatment group, injection site, and bodyweight category using appropriate descriptive statistics, based on the PK analysis set.

The natural log transformed primary PK parameters (eg, AUCinf, AUClast, and Cmax) will be analyzed using a mixed effects model with treatment, injection site, anti-COVID-19 vaccination status, and continuous baseline body weight on the log scale as fixed effects and participant as a random effect. Transformed back from the logarithmic scale, geometric means together with confidence intervals (CIs) (2-sided 95%) for AUCinf, AUClast, and Cmax, will be calculated and presented. Also, ratios of geometric means together with CIs (2 sided 90%) will be estimated and presented.

[figure not shown]

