2.2 Secondary Objectives

Secondary Objectives:

To examine the serum PK profiles of AZD7442 when administered as a single IM dose (co-formulation) (AZD8895 + AZD1061) and as two separate IM doses (AZD8895 and then AZD1061) (clonal cell line or cell pool material) of the individual mAbs in healthy adult participants

To further assess the safety of AZD7442 when administered as a single IM dose (co-formulation) (AZD8895 + AZD1061) and as two separate IM doses (AZD8895 and then AZD1061) (clonal cell line or cell pool material) of the individual mAbs in healthy adult participants

To evaluate the anti-drug antibody (ADA) responses to AZD7442 in serum following administration of a single IM dose as a co-formulation (AZD8895 + AZD1061) and as two separate IM doses (AZD8895 and then AZD1061) (clonal cell line or cell pool material) of the individual mAbs in healthy adult participants

Endpoint:

- T_{max} , AUC_{0-31d} , AUC_{0-61d} , t_{last} , and for final analysis AUC_{0-91d} , AUC_{0-181d} , $t_{1/2\lambda z}$, CL/F , and V_z/F
- AEs including serious AEs and AEs of special interest
- Laboratory assessments (hematology, clinical chemistry, and urinalysis)
- Physical examination
- Electrocardiogram
- Vital signs (systolic and diastolic blood pressure, pulse rate)
- Incidence and titers of anti-AZD8895 and anti-AZD1061 antibodies

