4.10.4 Primary Endpoint

The primary endpoints for evaluation of pharmacokinetic comparability will be assessed using a linear fixed effects analysis of variance model with the natural logarithm of primary PK parameters (eg, AUCinf [for final analysis only], AUClast, Cmax and AUC0-91d [for IA only]) for the individual mAbs AZD8895 and AZD1061, as well as for the sum of the individual mAbs of AZD7442 (AZD8895 + AZD1061) as the response variables, treatment, injection site, anti-COVID-19 vaccination status (as reported on the CRF), and continuous baseline body weight on the log scale as fixed effects and participant as a random effect.

Transformed back from the logarithmic scale, geometric least square means (GLSM) together with CIs (2-sided 95%) will be estimated and presented by treatment. Also, ratios of geometric least square means together with CIs (2-sided 90%) will be estimated and presented.

The following treatment comparisons will apply:

- Treatment A vs Treatment B
- Treatment A vs Treatment C
- Treatment B vs Treatment C

where:

- Treatment A: 300 mg (total protein) AZD7442 as a single IM dose (co-formulation of 150 mg AZD8895 + 150 mg AZD1061) (clonal cell line material).

- Treatment B: 300 mg (total protein) AZD7442 as two separate IM doses of the individual mAbs (150 mg AZD8895 and then 150 mg AZD1061) (clonal cell line material).
- Treatment C: 300 mg (total protein) AZD7442 as two separate IM doses of the individual mAbs (150 mg AZD8895 and then 150 mg AZD1061) (cell pool material).

One statistical model will be fitted for each PK parameter, including all study data. Estimating parameters for the comparisons listed above will be done from this one model making use of the appropriate contrasts.

A variance component covariance structure will be used for the within-participant errors. Degrees of freedom will be determined using Kenward-Roger approximation.

If the estimating algorithms do not converge, these covariance structures will be tried: first-order autoregressive, compound symmetry, unstructured and Toeplitz.

Missing values will not be imputed. In this analysis it is thus assumed that any missing values are missing at random (MAR).

The following figures, in black and white, will be generated:

Figure	Analysis set	Presented by

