4.10.5 Secondary Endpoints

4.10.5.1 PK Parameters

The following PK parameters will be listed and summarised by means of descriptive statistics:

- Tmax, AUC0-31d, AUC0-61d, tlast, and for final analysis AUC0-91d, AUC0-181d, $t_{1/2}/\lambda_z$, CL/F, and Vz/F
- Diagnostic parameters: λ_z , λ_z lower, λ_z upper, $\lambda_z N$, λ_z span ratio, Rsq adj, AUCextr

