4.13 Interim Analysis

There will be no interim analyses in the study.

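### Does the SAP's listing of AUC0-91d as a primary endpoint leave the comparability claim open?

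*SAP*

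**What the plan says.** The protocol synopsis, under Pharmacokinetic Endpoints, states "Primary PK parameters: AUCinf, AUClast, and Cmax" and then "Secondary PK parameters: Tmax, AUC0-31d, AUC0-61d, AUC0-91d, AUC0-181d, tlast". Protocol Tables 2-1 and 2-2 and Section 10.2 agree. The synopsis and Section 11.1.1 give the decision rule: the 90% confidence intervals for the geometric mean ratios of AUCinf (AUClast for some agencies) and Cmax must lie inside 0.8000 to 1.2500 for every comparison in the objectives.

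The SAP is less tidy:

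- Section 2.1 lists, for all three primary objectives, "AUC_{inf} (final analysis), AUClast, C_{max}, and AUC_{0-91d".
- Section 2.2 lists among the secondary endpoints "and for final analysis AUC_{0-91d} , AUC_{0-181d".
- Section 4.10.4 fits the comparability model to "AUCinf [for final analysis only], AUClast, Cmax and AUC0-91d [for IA only". The plot of individual parameters in its figure table carries the same tags.
- Section 4.10.5.1 gives listings and descriptive statistics for secondary parameters, including "for final analysis AUC0-91d, AUC0-181d".
- Section 4.13 states "There will be no interim analyses in the study", and Section 3.2 plans a final analysis only.

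**The concern.** Section 2.1 puts no interim-analysis tag on AUC0-91d, so on its face the parameter is primary at the final analysis. The model section then gives it no inferential analysis there, and SAP Section 4.14, which records departures from the protocol, does not mention it. A reader could conclude that a primary endpoint has been declared and left unanalysed. Alternatively, a further set of intervals might be counted or ignored once results are known. The trial is open label and SAP Section 4.10.4.2 makes no multiplicity adjustment, so an unsettled primary set would matter if it affected which intervals carry the claim.

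**Working it through.** **1. The role of AUC0-91d in the final analysis, section by section.**

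| Place | Role given |
|---|---|
| Protocol synopsis, Table 2-2, Section 10.2 | Secondary |
| SAP 2.1 | Primary, untagged |
| SAP 2.2 | Secondary, tagged for the final analysis |
| SAP 4.10.4, model and parameter plot | Interim analysis only |
| SAP 4.10.5.1 | Secondary, descriptive, tagged for the final analysis |
| SAP 4.14, additional subgroup PK analyses | Not included; AUCinf, AUClast and Cmax only |

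Section 2.1 stands alone. With no interim analysis, the remaining SAP sections give one result for the only analysis performed: AUC0-91d is listed and described, not tested.

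**2. Where the stray entry comes from.** The SAP amendment history records removal of the interim analysis on 08 Jul 2022. The same line of Section 2.1 still tags AUCinf for the final analysis, a tag that has a purpose only when there is a second analysis to distinguish. The protocol (Section 3.3.2) puts the half-life at about 90 days, so a 91-day area would be a natural interim stand-in for AUCinf. That last step is my inference. The documents do not state it.

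**3. Counting intervals.** There are 3 comparisons (A vs B, A vs C, B vs C) and 3 analytes (each antibody and their sum).

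- Reported as primary under the protocol: 3 × 3 × 3 parameters = 27.
- Reported as primary under SAP 2.1: 3 × 3 × 4 parameters = 36, a difference of 9.
- Deciding the claim for any one agency: 3 × 3 × 2 parameters (AUCinf or AUClast, plus Cmax) = 18 at most, taking all three analytes as required.
- Contribution of AUC0-91d to those 18: 0.

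**4. Error rate.** The claim requires every deciding interval to lie inside the limits. Call that event S, and let T be the event that the AUC0-91d intervals also pass. If AUC0-91d were added to the rule, the probability of a claim would be P(S and T), which cannot exceed P(S). The addition could make the claim harder to reach but could not inflate type I error. Leaving AUC0-91d out restores the protocol rule, which never contained it. Inflation would need a rule that let AUC0-91d replace a failed parameter, and neither document offers one.

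**5. Sample size.** The stated figure is at least 95% power with 69 per group, at a true ratio of 1. With σ = √ln(1 + CV²) and SE = σ√(2/69), approximate power is 2Φ(ln 1.25/SE − 1.645) − 1. For AZD1061 Cmax, CV = 38.5% gives σ = 0.372, SE = 0.0633 and power of about 94.0%. Exact values (136 degrees of freedom) are:

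| | AZD8895 | AZD1061 |
|---|---|---|
| Cmax | 96.7% | 93.8% |
| AUClast | 99.7% | 99.4% |
| AUCinf | 99.9% | 96.0% |

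The stated figure is reproduced to within about a point. The small shortfall for AZD1061 Cmax is unrelated to this question. Protocol Table 11-1 gives CVs for Cmax, AUClast and AUCinf only. AUC0-91d took no part in the sizing, and its power cannot be computed from the documents.

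**The case for a change.** The best argument for a change is that the SAP should settle its own primary list. Protocol Section 11.1.1 leaves the details of formal testing to the SAP, yet SAP Section 4.10.4 does not restate the decision rule and introduces the parameters as examples. Some outputs are defined by reference to the list. The figures of least-squares means and ratios cover the primary PK parameters, and the sensitivity analysis excluding two sites covers the primary PK endpoints. A programmer working from Section 2.1 would include AUC0-91d, and one working from Section 4.10.4 would not. The wording also survived two later SAP revisions (26 Jul 2023 and 27 Oct 2023).

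The inconsistency stands, and so does the small uncertainty about those outputs. The inference about the claim does not follow. The protocol fixes the rule in two places and the SAP states no competing one. If a programmer followed Section 2.1, the cost would be nine additional AUC0-91d intervals in the main analysis and their counterparts in the sensitivity analysis, none of which decides anything. The additional analyses in Section 4.14, modelled on Section 4.10.4, use the protocol's three parameters, so the team's working set is clear. SAP Section 4.10.4.1 also keeps the sponsor blinded to summary outputs until database lock, which limits any room for selection.

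**Conclusion.** No change to the plan follows. This is a clerical remnant of the removed interim analysis. It alters none of the deciding intervals, the error rate, the sample size or the conclusion; the most it could add is nine reported intervals that do not bear on the claim. An analyst reading the SAP with the protocol would treat AUC0-91d as secondary and descriptive, as SAP Sections 2.2 and 4.10.5.1 already do.

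This rests on the protocol's decision rule governing the comparability claim, since the SAP offers no other. One point cannot be checked: the SAP cites protocol Version 1.0 as its basis, and that version is not among the documents, so the status of AUC0-91d there is unknown. The current protocol is clear, and the conclusion depends on that text.

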2.2 Secondary Objectives

Secondary Objectives:

To examine the serum PK profiles of AZD7442 when administered as a single IM dose (co-formulation) (AZD8895 + AZD1061) and as two separate IM doses (AZD8895 and then AZD1061) (clonal cell line or cell pool material) of the individual mAbs in healthy adult participants

To further assess the safety of AZD7442 when administered as a single IM dose (co-formulation) (AZD8895 + AZD1061) and as two separate IM doses (AZD8895 and then AZD1061) (clonal cell line or cell pool material) of the individual mAbs in healthy adult participants

To evaluate the anti-drug antibody (ADA) responses to AZD7442 in serum following administration of a single IM dose as a co-formulation (AZD8895 + AZD1061) and as two separate IM doses (AZD8895 and then AZD1061) (clonal cell line or cell pool material) of the individual mAbs in healthy adult participants

Endpoint:

- T_{max} , AUC_{0-31d} , AUC_{0-61d} , t_{last} , and for final analysis AUC_{0-91d} , AUC_{0-181d} , $t_{1/2\lambda z}$, CL/F , and V_z/F
- AEs including serious AEs and AEs of special interest
- Laboratory assessments (hematology, clinical chemistry, and urinalysis)
- Physical examination
- Electrocardiogram
- Vital signs (systolic and diastolic blood pressure, pulse rate)
- Incidence and titers of anti-AZD8895 and anti-AZD1061 antibodies

2.3 Exploratory Objectives

Exploratory Objectives:

[figure not shown]
CCI

Endpoint:

- CCI

Exploratory Objectives:**Endpoint:**

3 INVESTIGATIONAL PLAN

3.1 Overall Study Design and Plan

This is an open label, randomized, three-arm, parallel group, single dose, study in healthy participants (males and females), performed at multiple study centers to assess pharmacokinetic (PK) comparability between different formulations of AZD7442, which is a combination of two individual monoclonal antibodies (mAbs), AZD8895 and AZD1061. Each participant will receive AZD7442 as either a single IM dose (co-formulation; AZD8895 + AZD1061) from a single vial or as two separate IM doses of the individual mAbs (AZD8895 and then AZD1061) from two separate vials from either clonal cell line material or cell pool material as follows:

- Treatment A: 300 mg (total protein) AZD7442 as a single IM dose (co-formulation of 150 mg AZD8895 + 150 mg AZD1061) (clonal cell line material).
- Treatment B: 300 mg (total protein) AZD7442 as two separate IM doses of the individual mAbs (150 mg AZD8895 and then 150 mg AZD1061) (clonal cell line material).
- Treatment C: 300 mg (total protein) AZD7442 as two separate IM doses of the individual mAbs (150 mg AZD8895 and then 150 mg AZD1061) (cell pool material).

Additionally, within each of the treatment groups, participants will be randomized 1:1:1 to one of the three injection sites:

- Lateral thigh,
- Gluteal dorsal,
- Gluteal ventral.

Further, participants will be stratified based on the body weight and vaccination status at randomization as follows:

[figure not shown]
- Body weight at randomization: < 70 kg; 70 to < 80 kg; and \geq 80 kg
- Anti-SARS-CoV-2 vaccination status at randomization: non-vaccinated or vaccinated (with one or more locally approved/authorized COVID-19 vaccine doses)

The study will comprise of:

- A Screening Period of up to 28 days that requires participants to visit the Clinical Unit (Visit 1).
- A Treatment Period of 1 day (Day 1; Visit 2) during which participants will be admitted to the study Clinical Unit and be randomized to receive their dose of IMP (AZD7442 as either a single IM dose or two separate IM doses). Participants will stay at the study clinic for at least 8 hours after dosing and will be discharged from the Clinical Unit at the discretion of the investigator, on the same day.
- A Follow-up Period of approximately 1 year consisting of regular visits to the study Clinical Unit starting from the day after dosing, Day 2 through to Day 361. The subsequent study visits total in 11 outpatient follow-up visits (Visits 3 to 13).

The end of study is defined as the last participant's last visit to the study Clinical Unit.

Figure 1 Study Schema

IM: Intramuscular

3.2 Planned Analyses

The details of the analyses planned during the conduct of this study is outlined in the following table.

Analysis	Trigger
Final Analysis	The data cut-off for final analysis will be after the last participant's last visit to the study Clinical Unit. The analysis will be performed after Clinical Database Lock.

4 STATISTICAL METHODS

4.1 Data Quality Assurance

All tables, figures and data listings to be included in the report will be independently checked for consistency, integrity and in accordance with standard Parexel procedures.

4.2 General Presentation Considerations

Analyses will be performed by Parexel, except for the derivation of the PK parameters, which will be performed by Labcorp.

Continuous data, if not otherwise specified, will be summarized in terms of number of non-missing observations (n), mean, standard deviation (SD), median, first quartile (Q1), third quartile (Q3), minimum, and maximum.

Categorical variables will be summarized using frequencies and percentages.

The minimum and maximum values will be reported to the same number of decimal places as the individual values. The mean, median, SD, Q1 and Q3 will be reported to one more decimal place than the raw data recorded in the database and the same level of precision will be used for standard error (SE), and confidence intervals (CI). In general, the maximum number of decimal places reported shall be four for any summary statistic.

Percentages will be presented to one decimal place. Percentages will not be presented for zero counts. Percentages will be calculated using n as the denominator. If sample sizes are small, the data displays will show the percentages, but any textual report will describe frequencies only.

Rounding should be the last operation in the treatment of data. There should be no rounding of intermediate results during the calculation of any derived value. Zeros at the end of a number should be retained.

All results will be presented by treatment period (if applicable) and overall with descriptive statistics.

CI and p-values, when presented, will generally be constructed at the 2-sided 95% level, if not stated otherwise in the specific analysis description.

P-values greater than or equal to 0.001, in general, will be presented to three decimal places. P-values less than 0.001 will be presented as “<0.001”. P-values equal to 1.000 will be reported as >0.999.

When change from baseline will be described, baseline is defined as the last reliable value prior to administration of the first dose of each treatment period.

Change from baseline will be defined as the value post-dosing minus the baseline defined, for each timepoint.

Percent change from baseline will be calculated as:

Percent change from baseline = ((visit value – baseline value)/baseline value) × 100

Depending on the extent of any impact, listings and/or summary tables of data relating to participants diagnosed with COVID-19 and impact of COVID-19 on study conduct (in particular missed visits, delayed or discontinued study intervention, and other protocol deviations) may be generated.

All other requirements and specifications for programming and presentation of TFLs will be specified in the TFL shells document.

